1. PROTOCOL SYNOPSIS

Title:	WALTZ: a prospective, non-significant risk, feasibility study to evaluate serial 90-minute applications of VibratoSleeve therapy to acutely increase the perfusion in peripheral arterial disease (PAD) subjects 65 years of age and older.
Design:	Prospective, single arm, open-label clinical trial to evaluate the feasibility of TUS in the treatment of early stage (Rutherford Class 1-3) PAD. The results of this study will be used to support future studies.
Device Name and Intended Use:	VibratoSleeve is an array of single element ultrasound transducers, driven in a phased manner, and held in place externally by an adjustable sleeve. In this study, the VibratoSleeve will be applied in clinic and will be tested to demonstrate evidence of an increase in distal limb perfusion in adults with PAD.
Visit Schedule:	Visits will occur at screening (baseline data) and at three in-clinic treatment sessions, each separated by at least a 1-week interval.
Study Objectives:	The objectives of this study are: 
• To determine the feasibility of VibratoSleeve therapy to acutely increase distal perfusion in peripheral arterial disease (PAD) subjects 65 years of age and over.• Collect data on tolerable acoustic dose of serial 90-minute TUS therapy in the treatment of early stage (Rutherford Class 1-3) PAD.• Evaluate subject feedback on wearability and tolerability of serial 90-minute TUS therapy.• Evaluate the nature, incidence, timing and resolution of all adverse events in subjects treated with VibratoSleeve as compared with historical data on current standard of care treatments for PAD.
Number of Subjects and Defined Point of Enrollment	A total of up to 12 subjects will be required to receive VibratoSleeve therapy. The point of enrollment is defined as the time the subject signs the Informed Consent Form (ICF) to undergo screening procedures to ascertain eligibility. It is anticipated that up to 50% of subjects enrolled in the study will meet the inclusion/exclusion criteria. Given the screen success rate, it is anticipated that approximately 24 subjects could be enrolled in the study to have 12 evaluable subjects qualified for the treatment and evaluation.

Inclusion Criteria	
1. Age \geq 652. Diagnosis of PAD.3. Claudication symptoms in Rutherford class 1, 2, or 3 as determined by the investigator.

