Exclusion Criteria	
1. Prior stenting in posterior tibial artery.2. Re-vascularization procedure within 30 days prior to enrollment in the study.3. Ulcers, cellulitis, or skin breakdown in treatment areas (posterior calf).4. History or diagnosis of severe chronic venous insufficiency.5. Acute limb ischemia within 30 days prior to treatment.6. History or diagnosis of deep venous thrombosis below the knee in treatment leg.7. Any conditions that, in the opinion of the investigator, may render the subject unable to complete the study or lead to difficulties for subject compliance with study requirements, or could confound study data.8. Subject's enrollment in another investigational study that has not completed the required primary endpoint follow-up period.
Safety Endpoint	All device and procedure related adverse clinical events experienced by subjects will be collected. Summaries of adverse events will be provided on a per subject and a per device basis. Severity and method of resolution will also be summarized. The number and primary reasons for medical or surgical interventions to treat device related adverse events will be summarized. This study is not powered to definitively evaluate the safety of the investigational device as compared to the historical data of comparable treatments for PAD.
Efficacy Endpoints	
The following parameters will be evaluated to assess performance of the VibratoSleeve TUS:
 
• The mean improvement in FlowMet perfusion rate as measured by the noninvasive FDA-approved imaging system FlowMet. Each subject's pre-treatment baseline perfusion rate will be calculated from at least 5 minutes (mean of 300 FlowMet measurements which are taken once a second) as Baseline period. The mean of the 90 minutes of the treatment period will then be normalized to the pre-treatment baseline to determine the percentage change in perfusion rate.• Tissue oxygen saturation and hemoglobin content as measured by the noninvasive FDA-approved imaging system Clarifi (StO₂). Clarifi measurements will be taken before (baseline), during and after treatment.

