	
• Ankle and Toe Brachial Indices (ABI, TBI). Improvement in ABI, TBI will be similarly compared for all subjects. ABI and TBI will be taken before and after each treatment• Quality of Life with VascuQoL and Walking Impairment Questionnaires 
Mean changes of all these endpoints from baseline during the treatment and to post-treatment will be analyzed.

Treatment	
In this protocol, therapy will be delivered at VISOC clinic during 3 separate visits with at least 1-week interval between each visit. TUS therapy will last for 90 minutes during each treatment visit.
 
Each subject will receive either low, medium or high acoustic intensity (varying peak negative pressure) of TUS at a treatment visit and all subjects will receive all 3 levels of intensity during the study.
 
Regular monitoring will be conducted to ensure subject compliance with therapy during treatment.
 
Subjects will be discharged from the study after Treatment Visit 3 or until any device or procedure adverse events are resolved or remain stable.

Statistical Hypothesis	Statistical hypotheses will not be applied in this pilot study. Tables and descriptive statistics of the subject demographic data, treatment parameters, and outcome variables will be generated at the completion of the study. Information collected during the study may be used to support a 510(k) application as well as to select the endpoints and determine sample sizes for future trials.
Study Duration	The Sponsor expects the trial to last six months from the time the first subject enrolls until the time of the last visit.

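### No contact is scheduled after Treatment Visit 3, so a related adverse event that starts after the third session would be found only if the subject reports it unprompted

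*Protocol*

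**What the plan says.** All references are to the Protocol, Section 1 (Protocol Synopsis).

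- **Visit Schedule row:** visits take place at screening and "at three in-clinic treatment sessions, each separated by at least a 1-week interval". No later visit or call is listed.
- **Treatment row:** "Subjects will be discharged from the study after Treatment Visit 3 or until any device or procedure adverse events are resolved or remain stable". The only monitoring described is for compliance while therapy is being given. Each subject gets a low, medium or high intensity at a visit, and "all subjects will receive all 3 levels of intensity during the study"; the order is not stated.
- **Efficacy Endpoints row:** "ABI and TBI will be taken before and after each treatment", and "Clarifi measurements will be taken before (baseline), during and after treatment". Staff therefore see the subject after every session, on the day.
- **Safety Endpoint row:** "All device and procedure related adverse clinical events experienced by subjects will be collected". The same row says that the study is not powered to evaluate safety definitively against historical data.
- **Study Objectives row, fourth objective:** "Evaluate the nature, incidence, timing and resolution of all adverse events in subjects treated with VibratoSleeve", compared with historical data on standard care.
- **Statistical Hypothesis row:** no hypotheses are applied, but "Information collected during the study may be used to support a 510(k) application".

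**The concern.** The discharge rule and the safety aims do not match. Keeping a subject until an event is resolved or stable requires that someone already knows of the event. It is a rule for following events, not for finding them. An event that begins at home after session 1 or 2 can be picked up at the next treatment visit. After session 3 there is no such occasion.

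The fourth objective concerns incidence and timing. If related events with later onset occur, those after the last session enter the data only by unprompted report, so later-onset incidence would tend to be understated and the observation window would differ between sessions. The loss is one of collection: no analysis plan can recover an event that nobody asked about. The data may be used for a regulatory submission and for planning later trials, so the gap would carry forward.

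**Working it through.** **Inputs from the protocol:** up to 12 treated subjects (Number of Subjects row); 3 sessions each, at least 1 week apart (Visit Schedule row); discharge after the third unless an event is open (Treatment row).

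**The plan's own figure.** The protocol gives no figure on adverse event follow-up. Its only derived number is the enrolment target: 12 / 0.50 = 24 subjects, which reproduces. Nothing below depends on it, and it is unrelated to the 24 sessions counted next.

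**Step 1: scheduled contact after each session.**
- Sessions: 12 × 3 = 36.
- Followed by a scheduled visit at least 7 days later (sessions 1 and 2): 12 × 2 = 24, or 67%.
- Followed by no scheduled contact (session 3): 12, or 33%.
- With one contact added after session 3: 36 of 36.

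Twelve subjects is a maximum. With fewer who complete all three sessions the counts fall, but the one-third share does not change.

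**Step 2: what this could mean for later-onset events.** Call an event later-onset if it begins after the subject leaves the clinic. The protocol gives no rate, so p per session is an assumption, shown at 5%, 10% and 20%. Further assumptions: p is the same at each session and independent between sessions; events after sessions 1 and 2 are found at the next visit; none is self-reported after session 3.

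- True proportion of subjects with at least one later-onset event: 1 − (1 − p)³.
- Proportion found: 1 − (1 − p)².
- Share of affected subjects missed: 1 − found / true.

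| p per session | True | Found | Of 12 subjects, true vs found | Share missed |
|---|---|---|---|---|
| 5% | 14.3% | 9.8% | 1.7 vs 1.2 | 31.6% |
| 10% | 27.1% | 19.0% | 3.3 vs 2.3 | 29.9% |
| 20% | 48.8% | 36.0% | 5.9 vs 4.3 | 26.2% |

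**Step 3: how far the assumptions matter.**
- *Same subjects react after every session:* each is found after session 1, so no subject is missed, but one third of the events still are.
- *Half of the post-session-3 events self-reported, p = 10%:* found = 1 − 0.9² × 0.95 = 23.1% against 27.1%, so about 15% missed rather than 30%.
- *All adverse events, with in-clinic onset always seen (also assumed rates):*
  - In-clinic 10% and later-onset 10% per session: true 1 − (0.9 × 0.9)³ = 46.9%; found 1 − 0.9³ × 0.9² = 41.0%; undercount 13%.
  - In-clinic 20% and later-onset 5%: true 1 − (0.8 × 0.95)³ = 56.1%; found 1 − 0.8³ × 0.95² = 53.8%; undercount 4%.

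**The case against.** The strongest reply is proportionality. The sleeve is worn externally for 90 minutes in clinic, the study is classed as non-significant risk, the aim is acute perfusion, no hypotheses are applied, and the Safety Endpoint row disclaims power for safety. Nothing in the protocol suggests that delayed harm is expected. This stands, and it limits the importance of the point. It does not remove it: lack of power concerns precision, whereas events that are not asked about bias incidence downward.

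A second reply is that only a synopsis is shown, and that the way events are elicited and the reporting window usually sit in a fuller safety section. This stands in part. The synopsis neither describes nor excludes a report by the subject after discharge, and it does not say how events are asked about at Treatment Visits 2 and 3. The split of 24 and 12 therefore counts scheduled visits, not proven ascertainment. But the visit list and discharge rule are explicit and leave no place for a later contact.

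Three stronger readings are tempting and not supported:
- *Events after session 3 will be lost.* The protocol does not rule out self-report; they are left to it.
- *Adverse event incidence will be understated by 26% to 32%.* That range concerns later-onset events only, at assumed rates. Events during the clinic stay can be observed at all 36 sessions, so the effect on total incidence is smaller.
- *The high intensity goes without follow-up.* The order is not stated. If it were balanced, 12 × 2/3 = 8 of 12 subjects would have later contact at each intensity; only one fixed order for everyone would give 12, 12 and 0. In-session tolerability can be observed at all three intensities either way.

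**Conclusion.** The point holds as a modest one. The stated schedule and discharge rule fall short of the stated safety collection: up to 12 of 36 sessions (33%) have no later scheduled contact, and a related event that begins after the subject goes home from session 3 would be found only by self-report. That count rests on the protocol alone.

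The effect on the results is unknown. The figure of 26% to 32% of affected subjects missed is an illustration that rests on assumed rates of 5% to 20%, independence between sessions, full detection after sessions 1 and 2, and no self-report. Relaxing these can lower it, to zero per subject if the same people react every time. The safety results are not invalidated. The change is worth making because it is cheap and because the missing information could not be recovered later.

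**What to change.** In the Visit Schedule and Treatment rows, add one telephone adverse event contact at least 7 days after Treatment Visit 3 and before discharge. State that the same adverse event questions are asked at the start of Treatment Visits 2 and 3 and on that call, so that each session has a comparable follow-up of at least 7 days. Let discharge follow the call, or come later if a device or procedure adverse event is still open.

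Cost: up to 12 telephone calls and about one more week in the study per subject. No extra subjects, clinic visits or treatments are needed, and the intensities, their order, the number of sessions and the interval between them stay as they are.
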